7.1 Subject Disposition

Subject disposition including numbers randomized, treated, and treatment discontinuation by reason, as well as the reasons for withdrawal from study will be summarized by treatment group using frequencies and percentages based on information collected on the relevant study case report form pages. The number of subjects screened, screen failures and reasons for failure will be summarized. The number of subjects randomized will also be tabulated by region, country, study site/investigator and treatment group. The number of subjects in each analysis set will be summarized by treatment group, when applicable. In addition, subject eligibility information including characteristics related to inclusion and exclusion criteria collected during screening will be summarized by treatment group.

Duration of follow-up will be calculated as the (date of the data cutoff – date of randomization) and will be summarized using mean, standard deviation, median, minimum, and maximum.

7.2 Demographic and Other Baseline Characteristics

Demographic and baseline characteristics include, but are not limited to age, sex, ethnicity, race, geographical region, response to initial intensive induction therapy, time since AML diagnosis, height, weight, body surface area (BSA), ECOG performance status, number and type of prior cancer therapies, cytogenetic risk levels, peripheral blood counts of hemoglobin, platelets, total white blood cells (WBCs) with blasts counts, BM blasts, and presence of baseline genetic mutations in several genes including, but not limited to, TP53, FLT3-ITD, NPM1, ASXL-1, RUNX-1, and CEBPA biallelic.

Categories of response to initial intensive induction therapy are defined as follows:

- Refractory is defined as refractory to induction where a subject did not have CR, CRp, or CRi to the first line induction regimen.
- First relapse refers to subjects who had just one prior regimen and had a response (CR, CRp, CRi, or PR) to the first line induction regimen.

• >1 relapse refers to subjects who had at least 2 prior regimens and had a response.

Time since diagnosis will be calculated as the (date of randomization – date of diagnosis). If the day is missing for date of diagnosis, the 15th of the month is used. If the month is missing, July 1st is used. If the year is missing, the date is left as missing.

Subject demographic and baseline characteristics will be summarized by mean, standard deviation, median, minimum, and maximum for continuous variables; and by counts and percentages for categorical variables. Both the Efficacy and Safety Analysis Sets will be used for the summaries.

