Patients unable to achieve a CR with standard induction therapy (refractory AML) or whose disease returns after achieving remission (relapsed) are likely to die from their disease (Estey 2012). Treatment strategy is directed towards getting the patient into remission and then to transplant. Otherwise, palliation is the goal. Patients whose first remission lasted longer than one year have a good chance at achieving a second remission with standard induction therapy and, if the transplant is successful, do almost as well as patients transplanted in first remission (Ossenkoppele et al 2016). There are no proven treatment options for subjects with AML refractory to intensive remission induction chemotherapy or for subjects who relapse after intensive chemotherapy treatment(s), particularly if they fail re-induction with the standard regimen. Safe and effective treatments prolonging survival and/or bridging to transplant are urgently needed for patients with relapsed or refractory (r/r) AML.

Choice of treatment for patients with r/r AML is based mostly on evidence from small studies and considers factors such as age, performance status, previous treatment history and responses, cytogenetics, access to care, and availability of medications (Roboz et al 2014). There are several commonly used salvage regimens, most of which include cytarabine as either a single agent or in combination regimens (NCCN AML Guidelines 2014), such as mitoxantrone, etoposide, and cytarabine (MEC) (Archimbaud et al 1991; Archimbaud et al 1995) and fludarabine, cytarabine, granulocyte colony-stimulating factor, and idarubicin (FLAG-Ida). The hypomethylating agents (HMAs) decitabine and azacitidine, though mostly studied in MDS and newly diagnosed AML (Kantarjian et al 2012, Fenaux et al 2010, Lubbert et al 2012), are often considered an option for frail, older patients with relapsed/refractory AML (Roboz et al 2014). Due to the lack of proven treatment for r/r AML, enrollment in a clinical trial is considered an appropriate strategy (NCCN AML Guidelines 2014; Roboz et al 2014).

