7.3.4 Subgroup Analysis

Subgroup analyses will be performed to explore how the treatment effect on OS is influenced by baseline variables, extent of treatment received, and the individual TC therapy administered. To evaluate the treatment effect at different levels of each of these variables, the Kaplan-Meier analysis and Cox model will be performed separately by each level of each variable as follows:

- Age ($<65, \geq 65$).
- Age ($<75, \geq 75$).
- Sex (Male, Female).
- Baseline cytogenetic risk (poor-risk, others).
- Baseline ECOG performance status (0-1, 2).
- Response to initial intensive induction therapy (refractory, first relapse, >1 relapse).
- Prior HCT (yes, no).
- Baseline BM blasts ($\leq 40\%$, >40%).

- Baseline PB blasts ($\leq 30\%$, >30%).
- Baseline total WBC counts ($\leq 20,000/\mu$ L, $> 20,000/\mu$ L).
- Study center region (North America, ROW).
- Race (White, Black, Asian, Other).
- Presence of baseline genetic mutations or gene expressions for each gene such as FLT3-ITD, NPM1, CEBPA biallelic, TP53, ASXL-1, and RUNX-1 (yes, no).
- Treatment cycles received (<4 cycles vs \geq 4 cycles).
- Treatment cycles received (<6 cycles vs \geq 6 cycles).
- Individual preselected TC (high intensity, low intensity, BSC).

The treatment effect (HR and 95% CI) for each of these subgroups will be displayed on Forest plots.

Subjects with missing a value for a variable used to define a subgroup will be excluded from that subgroup analysis except for subgroups with an "Other" category. In those subgroups, subjects with missing values will be included in the Other category.

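### SAP 7.2 places a partial response to first-line induction in two categories and defines >1 relapse by regimens, so the induction-response levels are neither exclusive nor true to their labels

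*SAP*

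**What the plan says.** SAP 7.2 gives three categories of response to initial intensive induction therapy.

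- *Refractory*: "Refractory is defined as refractory to induction where a subject did not have CR, CRp, or CRi to the first line induction regimen". The number of prior regimens plays no part.
- *First relapse*: subjects who "had just one prior regimen and had a response (CR, CRp, CRi, or PR) to the first line induction regimen". No documented relapse is required.
- *>1 relapse*: ">1 relapse refers to subjects who had at least 2 prior regimens and had a response". The text does not say which regimen the response must follow, which responses count, or how many relapses are needed.

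Neither SAP 7.2 nor 7.3.4 gives an order of precedence.

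The variable is used twice. SAP 7.2 summarises it "by counts and percentages for categorical variables", in both the Efficacy and Safety Analysis Sets. SAP 7.3.4 lists it as a survival subgroup, "Response to initial intensive induction therapy (refractory, first relapse, >1 relapse)", where "the Kaplan-Meier analysis and Cox model will be performed separately by each level of each variable as follows"; the results go on forest plots.

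For comparison, Protocol 1.2 describes the two disease states as "Patients unable to achieve a CR with standard induction therapy (refractory AML) or whose disease returns after achieving remission (relapsed)". SAP 1.2 describes them in the same way.

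**The concern.** A three-level variable should give each subject one level, and each level should mean what its name says. These definitions fail on both counts. PR is left out of the responses that rule out *Refractory* but is included among those that admit a subject to *First relapse*. The third level is named after relapses but defined by regimens.

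At stake is how the enrolled population is described and how one set of forest-plot rows is read. Apart from prior transplant, this is the only subgroup in SAP 7.3.4 that reflects prior treatment history; the Protocol 11.6.3 subgroup by number of prior regimens is not in the SAP list. The sponsor is not blinded (Protocol 6.2), so a rule for ambiguous subjects should be in writing before the tables are run.

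**Working it through.** The plan states no figure on this point, so there is none to reproduce. The check applies the three definitions literally to possible histories.

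**Inputs.** Best response to first-line induction (CR, CRp, CRi, PR or none) is crossed with three regimen histories: one prior regimen; two with no response to the later one; two with CR to the later one. That gives 5 × 3 = 15 profiles. Because the response in *>1 relapse* is unspecified, three readings are tried:

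- A: first-line CR, CRp or CRi only
- B: first-line response, including PR
- C: response to any regimen, including PR

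| First-line response | Prior regimens | Later response | Reading A | Reading B | Reading C |
|---|---|---|---|---|---|
| CR, CRp or CRi | 1 | n/a | First relapse | First relapse | First relapse |
| CR, CRp or CRi | 2 | none or CR | >1 relapse | >1 relapse | >1 relapse |
| PR | 1 | n/a | **Refractory and First relapse** | **Refractory and First relapse** | **Refractory and First relapse** |
| PR | 2 | none or CR | Refractory | **Refractory and >1 relapse** | **Refractory and >1 relapse** |
| None | 1 | n/a | Refractory | Refractory | Refractory |
| None | 2 | none | Refractory | Refractory | Refractory |
| None | 2 | CR | Refractory | Refractory | **Refractory and >1 relapse** |

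**Results.**

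1. Every profile gets at least one level. The number getting two is 1 of 15 under A, 3 under B and 4 under C. These count profiles, not subjects.
2. PR with one prior regimen gets two levels under every reading.
3. First-line CR, one relapse, then failed salvage (two regimens, one relapse) is labelled *>1 relapse* under every reading.
4. First-line non-response followed by a response to salvage falls in two levels only under C.
5. On the Protocol 1.2 description, a subject with PR only has not reached CR and is refractory. Calling that subject *First relapse* departs from the documents' own usage.

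**Size.** The share of subjects with an overlapping history is not given. For illustration only, with about 300 randomised (Protocol 4.1) and an assumed share p, the number in two levels is 300 × p and the percentages sum to 100 × (1 + p):

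| Assumed p | Subjects in two levels | Sum of percentages |
|---|---|---|
| 2% | 6 | 102% |
| 5% | 15 | 105% |
| 10% | 30 | 110% |
| 15% | 45 | 115% |

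The mislabelling in result 3 also cannot be sized. It concerns subjects with two or more prior regimens. In the Phase 2 relapsed/refractory cohort the median was 2 (Protocol 1.5.1.2, Table 1), so at least half had two or more. Protocol 4.2 calls the eligibility criteria similar. How many of those subjects had relapsed only once is not stated.

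**The case against.** The strongest defence is context. The categories stand under a heading about response to initial induction, and the *First relapse* line ties its response to the first-line regimen. Read that way, the response in *>1 relapse* is also to first-line therapy, and a first-line non-responder who later responded to salvage is simply *Refractory*. That is a natural reading, so this overlap is conditional. It does not rescue the PR case. Taking the three lines as a cascade would remove the overlap, but the mention of PR under *First relapse* would then do nothing. Nor does it help a subject with two regimens and one relapse.

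A reader might infer more than the documents support:

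- *The tables will double-count.* A single categorical variable ordinarily holds one value per subject. The outcome may instead be an undocumented assignment. The text settles neither.
- *The subgroup hazard ratios are invalid.* SAP 7.3.4 compares the arms within each level, and membership depends on history before randomisation. A subject meeting two definitions does not bias either comparison, provided that the assignment uses only that history. What is lost is a clean partition and an accurate label.
- *This is the trial's main prognostic feature.* SAP 3.1 uses the language of important prognostic factors for the stratification factors, and induction response is not one of them.

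It is also fair that SAP 7.2 summarises the number and type of prior therapies separately, and that the classification can be redone later from recorded data.

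**Conclusion.** The concern holds as a definitional fault with limited reach. Two parts are certain from the text: PR with one prior regimen meets two definitions with no precedence rule, and *>1 relapse* takes in subjects who have relapsed once. Overlap between *Refractory* and *>1 relapse* depends on a response that the SAP leaves unspecified.

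The consequence is confined to a baseline descriptor and one of 16 listed entries in an exploratory survival subgroup analysis. The variable is neither a stratification factor nor part of the test sequence in SAP 7.3.3, so the primary test and alpha control do not change. The number of subjects affected is unknown, and the percentages in the illustration are assumptions, not estimates. This is a minor correction, worth making because the written rule yields ambiguous or wrong labels and is easily repaired.

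**What to change.** Replace the three definitions in SAP 7.2 with levels applied in a fixed order:

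1. *Refractory*: no CR, CRp or CRi to first-line induction. PR belongs here, in line with the description of refractory disease in Protocol 1.2 and SAP 1.2.
2. *First relapse*: CR, CRp or CRi to first-line induction and one relapse.
3. *More than one relapse*: CR, CRp or CRi to first-line induction and two or more relapses.

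Under these rules the six PR and non-response profiles above fall only in level 1. The nine CR, CRp and CRi profiles divide between levels 2 and 3 by relapse count. If relapses cannot be counted reliably, keep level 1 and relabel the other two as first-line responders with one prior regimen and with two or more.

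State which regimen counts as first line, since Protocol 4.2 accepts qualifying induction given later. Use the same levels in SAP 7.3.4.

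The cost is a few lines of SAP text and one derived variable, settled before the final database lock described in SAP 6.0. Protocol 9.5.2 already records dates, best response and duration of response for prior anti-leukemic therapies, so no new data are needed.

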7.3 Efficacy Variables and Analyses

Unless otherwise specified, all efficacy analyses will be based on the Efficacy Analysis Set. This section describes the analyses conducted at the final and primary analysis time point after at least 12 months follow-up from the last subject randomly assigned to treatment. The stratification factors used in the analyses will be the randomization stratification factors unless it is necessary to collapse some strata due to analysis difficulties caused by too many strata. The rule for collapsing strata are detailed in Section 7.3.5. If the strata are collapsed for the analysis of the primary endpoint, the collapsed strata will be applied to stratified analyses for all subsequent endpoints.

7.3.1 Primary Efficacy Endpoint and Analyses

OS is the primary efficacy endpoint and is defined as the time, in days, from the subject randomization date to the date of death (regardless of cause).

Survival time in days = (date of death or censoring – date of randomization)

In the absence of death at the time of analysis, the survival time will be censored on the last date the subject is known to be alive. Subjects who do not have post-baseline information will be censored at the date of randomization.

OS curves will be estimated using the Kaplan-Meier method and formally compared between the two treatment groups using a 2-sided stratified log-rank test, stratified by the randomization stratification factors.

The null and alternative hypotheses are:

- Null hypothesis H₀: Survival curves are the same between the two treatment arms
- Alternative hypothesis H₁: Survival curves are different between the two treatment arms

OS will be tested at an overall alpha level of 0.05, as further described in Section 7.3.3. If this primary endpoint reaches statistical significance at this level in favor of guadecitabine, then the study will be considered positive for efficacy.

The median (and quartiles) duration of OS and the associated 95% CI for each treatment arm will be estimated using the Kaplan-Meier method and the log-log transformation for the survival function.

In addition, the HR and its 95% CI will be estimated using a Cox proportional-hazard model with treatment group as the independent variable and stratified by the same randomization stratification factors as used for the log-rank test.

The following sensitivity analyses will be conducted for the primary efficacy endpoint of OS for evaluating robustness of the treatment effect:

- 1) OS will be analyzed using Kaplan-Meier method and compared between the guadecitabine and TC using log-rank test without stratification.
- 2) An "as-treated" analysis will be conducted for OS, based on treatment actually received as described in Section 5.2, using the same Kaplan-Meier method and 2-sided stratified log-rank test described above. Subjects who were randomized but not treated will not be included in this analysis.
- 3) An analysis will be conducted using the same Kaplan-Meier method and 2-sided stratified logrank test described above. However, the survival time will also be censored on the date the subject receives other anti-leukemia treatments (except hematopoietic cell transplant [HCT]).

7.3.2 Secondary Efficacy End Points and Analyses

Secondary efficacy endpoints include EFS, survival rate at 1 year and 2 years after randomization, NDAOH, transfusion independence rate, combined CR + CRh rate, CRc rate and HCT rate, duration of combined CR and CRh, and the EQ-5D-5L descriptive system and the EQ VAS.

7.3.2.1 Event-Free Survival

Event-free survival (EFS) is defined as the time, in days, from the subject randomization date to the earliest of treatment discontinuation (for reasons other than initiation of HCT), start of alternative anti-leukemia therapy (other than HCT), or death.

In the absence of any of these events at the time of analysis, event-free survival time will be censored on the last date the subject is known alive. Subjects who do not have post-baseline information will be censored at the date of randomization.

EFS curves will be estimated using the Kaplan-Meier method and formally compared between the two treatment groups using a 2-sided log-rank test, stratified by the randomization stratification factors. EFS will be tested at an overall alpha level of 0.05, as further described in Section 7.3.3.

The median (and quartiles) duration of EFS and the associated 95% CI for each treatment arm will be estimated using the Kaplan-Meier method and the log-log transformation for the event-free survival function.

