7.4.1 Supportive, Prophylactic, or Other Treatments

Supportive care will be allowed in all study arms according to institutional standard practice. Hydroxyurea may be added to any of the TC options to control proliferative disease as part of study treatment. Hydroxyurea is allowed after randomization in the guadecitabine arm in the first 30 days of treatment. If it is given to guadecitabine subjects after the first 30 days, it should be recorded as a deviation but the subject can still continue on guadecitabine study treatment. Intrathecal treatment to control CNS disease is allowed for all subjects as a concomitant treatment. Supportive care includes, but is not limited to treatment with hydroxyurea, blood transfusions (RBCs or platelets), growth factors including erythropoiesis stimulating agents (ESAs), granulocyte stimulating factors (GSFs), iron chelating therapy, and broad spectrum antibiotics and/or antifungals. The investigator is permitted to prescribe supportive treatment(s) at his or her discretion. Give supportive treatment according to the institutional standard practice or other established standard of care guidelines. Investigators are also allowed to give donor lymphocytes infusion (DLI) if it is part of their standard practice in certain subjects with r/r AML. Any supportive or other concomitant treatment should be documented in the provided CRFs/eCRFs.

During treatment cycles of guadecitabine 10-day regimen and all high intensity regimens in the TC arm, prophylactic broad spectrum antibiotics and prophylactic broad spectrum antifungal treatment, with activity against *Aspergillus* species, such as posaconazole and voriconazole are highly recommended.

Once the subject is permanently discontinued from their study treatment due to progression, unacceptable toxicity, bridged to transplant, or any other reason, all subsequent anti-leukemia therapy including HCT or hydroxyurea will be recorded as subsequent anti-AML therapy.

7.4.2 **Prohibited Medications**

Other anticancer therapies, unless specified in the protocol (eg, endocrine therapy described in exclusion criteria), are not to be used. Cytotoxic chemotherapy and investigational treatments are prohibited for as long as subjects remain on study treatment.

Vaccination with live vaccines is prohibited while subjects remain on study treatment.

7.5 **Overdose Instructions**

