11.6.2.1 Event-free Survival (EFS)

EFS is defined as the number of days from randomization to the earliest of disease progression, treatment discontinuation, start of alternative anti-leukemia therapy (except for HCT), or death.

Disease progression is defined as earliest occurrence of one of the following:

- For subjects with CR, CRh, CRi, or CRp, the confirmed (at least 2 PB samples at least 1 week apart) appearance of ≥5% leukemic blasts in PB, OR ≥5% leukemic blasts in the BM.
- For all other subjects, when PB or BM shows evidence of continued increase in blasts % that necessitates alternative therapy.

EFS will be displayed using a Kaplan-Meier estimate and will be compared between the two treatment groups using a log-rank test stratified by the randomization stratification factors. EFS time will be censored on the last date the subject is known to be alive without an EFS event.

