1.0 INTRODUCTION

This Statistical Analysis Plan (SAP) is based on SGI-110-06 protocol version 4.0, dated 29 October 2018. Based on data from 278 randomly assigned subjects, the Data Monitoring Committee (DMC) recommended stopping further enrollment into the trial based on futility analysis that indicated the trial was unlikely to show superiority of guadecitabine over treatment choice (TC) for overall survival (OS). Consequently, the study was closed to further enrollment in September 2018 (protocol amendment 4).

Analyses and statistical reporting for SGI-110-06 will be conducted by Astex Pharmaceuticals Biostatistics department with the interim analysis results as reported by the study's DMC. The analyses specified in this document supersede the high-level analysis plan described in the protocol.

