3.2.2 Secondary Efficacy Endpoints

- EFS defined as the number of days from randomization to the earliest date of, treatment discontinuation (for reasons other than initiation of HCT), start of alternative anti-leukemia therapy (except for HCT), or death.
- Survival rate at 1 year after randomization. (Subjects will also be followed long term to estimate 2-year survival rate.)

- NDAOH.
- Transfusion independence rate, calculated based on the number of subjects with neither red blood cell (RBC) nor platelet transfusion for any period of 8 weeks after treatment.
- CR rate based on modified International Working Group (IWG) 2003 AML Response Criteria and CRh rate as described in the US FDA approved Prescribing Information of enasidenib and ivosidenib.
- CRc (CR+CRi+CRp) rate.
- HCT rate. (In subjects who undergo HCT, time to stem cell engraftment and 100-day mortality rate post HCT will also be assessed.)
- Duration of combined CR and CRh, defined as the time from first CR or CRh to time of relapse.
- Health-related QOL by EQ-5D (consisting of the EQ-5D-5L descriptive system and the EQ visual analogue scale [VAS]).

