Subjects who did not receive any study treatment, or who do not have a valid post-treatment (or post C1D1 visit date for BSC) efficacy assessment (ie, no post-treatment BM/PB sample or the quality of BM/PB sample is not adequate for an assessment of efficacy) will be classified as not evaluable (NE) for response classifications. These subjects will be included in the denominator of the ITT analysis for calculation of response rates. Subjects who cannot be classified into a response category (CR, CRp, CRi, CRh, or PR) or into the NE category will be classified as non-responders (NR) for a given evaluation time point. For subjects who experience different response levels at different visits, the best response in the order of CR, CRp, CRi, and PR will be used for summary and analyses. Subjects who progress (see Section 7.3.2.1 for definition) prior to experiencing a response (CR, CRp, CRi, CRh, or PR) will be included in the NR category. The best response (CR, CRp, CRi, PR, NR, or NE) based on the investigators will be summarized in a table displaying the number and percentage of subjects who meet the criteria for each endpoint. CRh, which is a subcategory of CRp and Cri, will be summarized similarly.

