7.3.2.9 Duration of Combined CR and CRh

A combined duration of CR and CRh (in number of days) will be calculated from the first time a CR or CRh is observed to the date of the earliest of the following 3 events: (1) relapse (defined as the earliest time point whereby BM assessment or PB assessment by the investigator indicate relapse/disease progression due to confirmed reappearance of leukemic blasts in PB or $\geq 5\%$ leukemic blasts in BM, or clinical progression determined by the investigator), (2) start of alternative therapy (except HCT) or (3) death. In the absence of any event, the combined duration of CR and CRh will be censored at the last available time point (BM assessment, PB assessment, or safety/long-term follow-up visit) at which an event was not observed. Duration of combined CR and CRh will be analyzed using the Kaplan-Meier method for subjects who achieved a CR or CRh during the study and compared between the two treatment groups using a non-stratified log-

rank test. The median and quartiles of duration of complete response, as well as their respective 95% CIs will be provided. Duration of CR will be calculated and analyzed similarly.

To take the proportion of responders into consideration when analyzing duration of combined CR and CRh, a separate analysis including all subjects will be conducted with a 0-day event duration assigned to subjects who did not achieve a CR or CRh. The median and quartiles of duration of complete response, as well as their respective 95% CIs will be provided.

In addition, both time to first response and time to best response will be calculated and analyzed for subjects who achieve a response of CR, CRp, CRi, or PR. Time to first response is defined as the time, in days, from the date of first treatment (C1D1) to the first date when any response is achieved. Time to best response is similarly defined as the time, in days, from the date of first treatment (C1D1) to the first date when a subject's best response, in the order of CR, CRp, CRi, or PR, is achieved. The times to first response and best response will be summarized by treatment group using mean, standard deviation, median, minimum, and maximum. Time to CR will be summarized similarly.

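### The SAP's EFS definition omits disease progression and relapse, which the protocol counts, and leaves a cross-reference to a progression definition that is not there

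*SAP*

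**What the plan says.** Protocol 11.6.2.1 states that "EFS is defined as the number of days from randomization to the earliest of disease progression, treatment discontinuation, start of alternative anti-leukemia therapy" (HCT excepted), or death. The synopsis and sections 4.3.2 and 11.6.2 give the same list. Section 11.6.2.1 then defines progression in two parts. For subjects in CR, CRh, CRi or CRp it is confirmed blasts of at least 5% in blood, or at least 5% in marrow; this is relapse. For everyone else it is a continuing rise in blasts that makes alternative therapy necessary. On censoring it says: "EFS time will be censored on the last date the subject is known to be alive without an EFS event".

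SAP 7.3.2.1 counts the "earliest of treatment discontinuation (for reasons other than initiation of HCT), start of alternative anti-leukemia therapy (other than HCT), or death". SAP 3.2.2 has the same three events and reads "earliest date of, treatment discontinuation (for reasons other than initiation of HCT", with a comma standing where the protocol's first event stood. If none of the three occurs, SAP 7.3.2.1 censors at the last date known alive. SAP 1.0 settles precedence: "The analyses specified in this document supersede the high-level analysis plan described in the protocol".

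Three other passages bear on the point:
- SAP 7.3.2.5, on classifying non-responders, refers to "Subjects who progress (see Section 7.3.2.1 for definition) prior to experiencing a response".
- Protocol 5.4.1 keeps best supportive care (BSC) subjects on study treatment until they progress.
- Protocol 7.4.1 treats transplant as a permanent stop: "Once the subject is permanently discontinued from their study treatment due to progression, unacceptable toxicity, bridged to transplant, or any other reason".

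**The concern.** A component of the first secondary endpoint disappears between protocol and SAP, and the visible text does not say why. Protocol 11.6.2 leaves fuller definitions to the SAP, but removing an event is not a fuller definition. The comma in SAP 3.2.2 and the dead reference in SAP 7.3.2.5 are what an incompletely edited deletion would leave behind.

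Two things are at stake. First, progression is still used in the SAP but no longer defined for subjects who have not responded. It enters the non-responder category. For BSC subjects it also decides when the retained event, treatment discontinuation, occurs. Second, some relapsed subjects will be shown as event-free on the EFS curve until something else happens to them.

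**Working it through.** The documents give no EFS event count, power or effect size, so there is no plan figure to reproduce. The check is a comparison of texts, followed by an illustration of size.

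**Step 1. Event lists side by side.**

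| Event | Protocol 11.6.2.1 | SAP 3.2.2 and 7.3.2.1 |
|---|---|---|
| Progression, including relapse | yes, defined | no |
| Treatment discontinuation | yes | yes, unless to start HCT |
| Alternative therapy other than HCT | yes | yes |
| Death | yes | yes |

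**Step 2. Is progression defined elsewhere in the SAP?** Section 7.3.2.9 measures response duration "to the date of the earliest of the following 3 events: (1) relapse" and describes relapse there, but only for subjects who reached CR or CRh. It cannot serve 7.3.2.5, which concerns progression before any response.

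**Step 3. Which progressions does the SAP list miss?**
- Non-responders: protocol progression presupposes a need for alternative therapy, which the SAP counts. Largely captured.
- Progression on treatment: this normally ends treatment, which the SAP counts. Captured.
- Relapse after HCT, either arm: the stop for HCT is exempt and has already happened, so the next possible event is alternative therapy or death. Missed until then.
- Relapse after a completed TC course: missed until alternative therapy, a later recorded discontinuation, or death.

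**Step 4. Size, with the same disease in both arms** (true HR 1; HR is guadecitabine/TC; completing TC is not an event).

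*Calculation A.* From the documents: 23.3% responders (protocol Table 2). Assumed:
- median OS 5.2 months;
- non-responder progression median 2.5 months, always an event;
- remission median 8 months from month 1.5;
- mean survival after relapse 1.65 or 3.5 months;
- TC course complete at 1.5–2.5 or 3–5 months;
- new therapy after relapse in 90% (mean delay 0.5 months) or 50% (mean delay 1.5 months);
- censoring at 12–32 months.

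| TC responders on a finite course (assumed) | EFS HR, SAP list |
|---|---|
| 25% | 1.00–1.02 |
| 50% | 1.01–1.03 |
| 100% | 1.01–1.07 |

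The TC median moves by 0 to +0.17 months and TC 12-month EFS by +0.1 to +2.2 points. Relapse after completion is counted 0.5–2.3 months late on average. If all such relapses lead to a recorded discontinuation, HR is 1.00; if mean survival after relapse were 9 months, the top would be 1.12. HCT in 20% or 40% of responders in both arms gives HR 1.00 and +0.1 to +0.9 points at 12 months; 40% against 20% shifts HR by about 0.01 or less.

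*Calculation B.* Broader, all inputs assumed: median 2.5 months to progression, 3 months from progression to death, alternative therapy in half at 14 days after progression, and 25–50% of all TC subjects (not only responders) on a course ending at day 28, 56 or 112. The SAP list gives HR 1.09–1.24. The protocol list gives 0.97–1.03 where the truth is 1, which shows the simulation error.

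*Why they differ.* In A the affected share of TC is at most 0.233 × 25%, 50% or 100% = 5.8%, 11.7% or 23.3%. In B the progression time has mean 2.5 × 30.4 / ln 2 = 109.6 days, so exp(−28/109.6) = 77.5% are progression-free at day 28 and exp(−112/109.6) = 36.0% at day 112. The affected share runs from 0.25 × 36.0% = 9% to 0.50 × 77.5% = 39%. B also lets half of progressing subjects, including non-responders, go without alternative therapy, which fits poorly with the protocol's non-responder definition. I read B as the high side.

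**The case against.** The strongest reply is that the omission hardly matters and may be deliberate. Recorded discontinuation, new therapy and death are harder dates than open-label progression; most progression reaches EFS through them; and EFS is tested only if OS succeeds (SAP 7.3.3), in a trial whose enrollment stopped for OS futility. The point about size stands. It does not repair the dead reference or the undefined term. A deliberate choice would also need a stated reason. One in removed text cannot be excluded.

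A reader might infer more than the documents support:
- *That EFS now contradicts the CR/CRh duration analysis.* They are different endpoints and may have different events; duration, for its part, does not count treatment discontinuation.
- *That the SAP's censoring wording is a separate error.* Under the SAP's own list it is close to the protocol's. The difference matters only once progression is restored.
- *That EFS is heavily biased toward guadecitabine.* That would follow only from scoring planned TC completion as discontinuation, which the protocol also leaves open. In calculation B that scoring gives HR 0.67–0.94, identical under either event list, so none of it measures the omission.
- *That the change was made for advantage.* Nothing in the text shows motive, and the omission by itself pushes the HR slightly against guadecitabine.

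**Conclusion.** The SAP's EFS definition should be corrected. It drops an event that the protocol lists and defines, gives no visible reason, and leaves SAP 7.3.2.5 pointing at nothing. Followed as written, it shows subjects who relapse after HCT or after a completed TC course as event-free for longer than the protocol would.

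The consequence is modest. It falls on the reported EFS curves and later EFS rates. The null HR is about 1.00–1.07 on the responder-based inputs and 1.09–1.24 on the broader ones; both rest on assumed disease and treatment-course inputs and are illustrative only. Because of the OS gate, an effect on a confirmatory claim is unlikely.

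A secondary point, inherited from the protocol and not part of the SAP error: neither document says whether completing a planned TC course without progression is a treatment discontinuation. Protocol 7.2 suggests not, since new therapy after completion is what then requires discontinuation. Sections 7.4.1, 9.5.5 and 9.5.6 leave doubt, because they recognise any reason for stopping and tie the safety visit and long-term follow-up to discontinuation. Scoring completion as an event would move the EFS HR toward guadecitabine with no true difference.

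**What to change.** In SAP 3.2.2 and 7.3.2.1:
1. Restore disease progression/relapse as an EFS event, with the two-part definition from protocol 11.6.2.1. This also repairs the reference in 7.3.2.5 and gives the BSC discontinuation date a defined basis.
2. Restore the protocol's censoring rule, so that follow-up ends at the last date known alive and free of an EFS event.
3. Keep the exemption for discontinuation to start HCT.
4. Report the current SAP event list as a sensitivity analysis, with EFS events tabulated by type and arm.
5. As a clarification, state whether planned TC completion without progression counts as treatment discontinuation.

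If the sponsor prefers the current list as primary, it should give the reason and place a progression definition where 7.3.2.5 points.

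The cost is SAP wording and programming. Reasons for discontinuation are recorded (protocol 5.4.1), and progression assessments continue after discontinuation (protocol Table 7 footnotes and 9.5.6). The downside is that progression dates depend on visit timing and open-label investigator assessment. Some will be late or missing, because long-term visits may be by telephone and subjects may refuse assessments (protocol 9.5.6). The change also does not remove the asymmetry between open-ended guadecitabine and finite TC courses that arises while discontinuation for other reasons remains an event.
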